03 NOV 2020

Version 11.0

Page: 49 of 259

Table 9–1: Schedule of procedures and assessments in part 1 – Study 16027

Phase	Screening	Treatment Phase				Fol	Follow-up Phase				
Visit	1	2	3	4 ^a	5 ^a	6	7 ^a	8 (EOT) ^b	9	10	11
Day	-14 to -1	1 °	7 ± 1	14 ± 1	21 ± 3	30 ± 3	42 ± 3	60 ± 3	90 ± 7	240 ± 7	420 ± 7

^p At Visit 6 (Day 30), subjects will return all remaining study drug and empty packaging, and study drug for the remaining 30 days of treatment will be dispensed.

^q A pre-paid phone card will be provided at Visits 3 and 6 to facilitate contact between study site personnel and the subjects/subjects' authorized representatives at Visits 4, 5, and 7.

* IHA will be performed at Visit 1 and Visit 11 only, if adequate specimens are available

03 NOV 2020

Version 11.0

Page: 50 of 259

Table 9–2: Schedule of procedures and assessments in part 2 – Study 16027

	FU Visit 1 Year ^a 2 (± 6 weeks)	FU Visit 2 Phone Follow-up Year 2.5 (± 6 weeks)	FU Visit 3 Yearª 3 (± 6 weeks)	FU Visit 4 Phone Follow-up Year 3.5 (± 6 weeks)	FU Visit 5 Yearª 4 (± 6 weeks)
Informed consent/assent	•				
Inclusion/exclusion criteria	•				
Concomitant medications	•	•	•	•	•
Recombinant ELISA, total purified antigen ELISA, non- conventional ELISA	•		•		•
IHA	•		•		•
qPCR test	•	●d	•	●d	•
Physical examination	•		•		•
Clinical signs or symptoms of Chagas' disease	•	•	•	•	•
Body weight and height/length	•		•		•
Vital signs (systolic blood pressure, diastolic blood pressure, pulse)	•		•		•
12-lead ECG ^c	•		•		•
Adverse events ^b	•	•	•	•	•
Inquiry of housing conditions (exclusion criterion #3)	٠	•	•	•	٠

a The year of each visit will be relative to the end of treatment in part 1 (CHICO). b Adverse events considered at least possibly related to nifurtimox and adverse events caused by protocol-required procedures.

c In case of abnormalities suspicious for cardiac involvement, further diagnostic examinations will be performed.

d At the discretion of the investigator in case of suspected reinfection or reactivation of Chagas' disease (unscheduled study visit).

03 NOV 2020 Version 11.0

Page: 51 of 259

9.2 Visit description

9.2.1 Screening

9.2.1.1 Visit 1 – screening visit (Days -14 to -1)

No study-specific procedures will be performed before the subject/legally authorized representative signs the informed consent form, or a minor subject provides assent, including asking a potential subject to fast (if applicable, depending on the age of the subject at the discretion of the investigator) prior to the screening blood samples. Informed consent/assent for optional PK blood sampling will also be obtained. After the consents/assents have been obtained, the following assessments will be performed:

- Collection of demographic data
- Medical and surgical history, including date of menarche for female subjects, and method of contraception
- Evaluation of inclusion and exclusion criteria
- Assessment of Chagas' disease signs and symptoms (to be performed during physical examinations); see Section 9.4.4
- Concentration test for *T. cruzi* (subjects <8 months of age at randomization) and conventional serologic testing for Chagas' disease (subjects ≥ 8 months < 18 years of age) conducted in local laboratory (or acceptable documentation of positive Chagas' disease within 3 months prior to screening and no prior anti-trypanocidal or anti-parasitic treatment). Specimens taken for conventional serology, non-conventional serology, IHA, and qPCR will be frozen and stored at -20°C prior to shipment to the central laboratory where they will be stored at -70°C.^{117,118}
- Assessment of pretreatment AEs and concomitant medications
- A complete physical examination of body systems. Abnormal findings will be documented as medical history (see Section 9.6.1.1).
- Neurological examination (see Section 9.6.3.3). Abnormal findings will be documented as medical history (see Section 9.6.1.1).
- Vital signs (blood pressure is optional in subjects < 5 years of age at the discretion of the investigator), height/length, and weight
- 12-lead ECG (optional in subjects < 5 years of age at the discretion of the investigator)
- Serum hematology and chemistry, coagulation, and urinalysis (if urine specimen can be obtained). Fasting is dependent on the age of the subject at the discretion of the investigator.

¹¹⁷ Modified as per Amendment 2 and Amendment 5.

¹¹⁸ Replaced IFA with IHA per Amendment 6.

03 NOV 2020

• Urine pregnancy test on all females of childbearing potential (i.e., those who have experienced menarche). Any subject with a positive urine pregnancy test will have a serum pregnancy test to confirm results; if pregnancy is confirmed, the subject is to be excluded from study participation.¹¹⁹

9.2.2 Treatment phase

9.2.2.1 Visit 2 – baseline (treatment phase, Day 1)

Version 11.0

Visit 2 will take place after all laboratory test results and assessments performed at the Screening Visit are available. The following assessments will be performed:

- Re-evaluation of inclusion and exclusion criteria
- Assessment of pretreatment AEs and concomitant medications
- Vital signs (blood pressure is optional in subjects < 5 years of age at the discretion of the investigator), height/length, and weight
- 12-lead ECG (optional in subjects <5 years of age at the discretion of the investigator).
- Urine pregnancy test on all females of childbearing potential (i.e., those who have experienced menarche). Any subject with a positive urine pregnancy test will have a serum pregnancy test to confirm results; if pregnancy is confirmed, the subject is to be excluded from study participation.
- For subjects consenting to PK assessments, a pre-dose PK blood sample will be obtained (see Table 9–1).
- Administer first dose of study drug to all subjects
- For subjects consenting to PK assessments, post-dose PK blood samples will be obtained (see Table 9–1). At the 2 4 hour time point of PK blood sampling (i.e., at the time of C_{max}), an ECG will be obtained to allow for PK/PD investigations.¹²⁰ Dispense study drug and diary with instructions for use. Subjects consenting to optional PK assessments will be instructed to withhold taking study drug on the morning of Visit 3 and to complete the PK subject diary, according to the instructions provided on the PK subject diary .¹²¹; subjects not consenting to optional PK assessments may take their study drug on the day of Visit 3 as instructed. The PK subject diary has been added in order for the PK subjects to record all foods they consume when taking each dose of study drug, along with the times they eat each meal. Examples of these entries, based on foods typically consumed in South American countries, will be given to each subject at the PK study sites.¹²²

¹¹⁹ Text added/deleted/modified for clarity and to reflect changes made per Amendment 1

¹²⁰ Added as per amendment 2.

¹²¹ Text modified as per amendment 4

¹²² Text modified as per amendment 4

03 NOV 2020

• Subjects and/or their legally authorized representatives will be advised of the possibility of change in the subject's urine color due to the ingredient riboflavin. Depending on the country, study site personnel may dispense condoms at the time that study drug is dispensed to either the subject or the subject's parent/legal guardian, with an explanation of rationale and risks.¹²³

9.2.2.2 Visit 3 (Day 7 ± 1 days)

- Assessment of Chagas' disease signs and symptoms (to be performed during physical examinations); see Section 9.4.4
- Concentration test for *T. cruzi* (subjects < 8 months of age), conventional and nonconventional serologic testing for Chagas' disease, and qPCR
- Assessment of AEs
- Concomitant medications
- Brief physical examination, including assessments of heart, lungs, and abdomen, skin for the presence of severe dermatitis, and clinical assessments for the presence of peripheral neuropathy. Abnormal findings will be documented as AEs (see Section 9.6.1.1).
- Neurological examination (see Section 9.6.3.3). Abnormal findings will be documented as AEs (see Section 9.6.1.1).
- Vital signs (blood pressure is optional in subjects < 5 years of age at the discretion of the investigator), height/length, and weight
- 12-lead ECG (optional in subjects < 5 years of age at the discretion of the investigator).
- Serum hematology and chemistry, coagulation, and urinalysis (if urine specimen can be obtained). Fasting is dependent on the age of the subject at the discretion of the investigator.
- Urine pregnancy test on all females of childbearing potential (i.e., those who have experienced menarche). Any subject with a positive urine pregnancy test will have a serum pregnancy test to confirm results; if pregnancy is confirmed, the subject is to be discontinued from the study and undergo all study assessments as described in the EOT Visit.
- For subjects consenting to PK assessments, a pre-dose PK blood sample will be obtained (see Table 9–1).

¹²³ Text added/deleted/modified for clarity and to reflect changes made per Amendment 1

03 NOV 2020

Page: 54 of 259

- Administer study drug with food to subjects consenting to PK assessments (who withheld their morning dose of study drug) and instruct subject on completion of PK diary, according to the instructions provided on the PK subject diary.¹²⁴
- For subjects consenting to PK assessments, post-dose PK blood samples will be obtained (see Table 9–1). At the 2 4 hour time point (i.e., at the time of C_{max}), an ECG will be obtained.
- Collect study drug and diary. Additional diaries may be provided if necessary.
- Drug accountability and review of diaries for study drug compliance
- Dispense pre-paid phone card to facilitate contact between study site personnel and the subjects/subjects' authorized representatives at Visit 4.¹²⁵

9.2.2.3 Visit 4 (Day 14 ± 1 days)

Study site personnel will contact the subject/legally authorized representative via telephone to assess for the occurrence of AEs, use of concomitant medications, compliance with study drug administration, and completion of subject diary or PK subject diary¹²⁶. A Phone Contact Form for the telephone contacts to obtain safety and compliance information will be provided to all sites (Section 16.1). If any safety concern arises, subjects may return to the study site for an Unscheduled Visit.¹²⁷

9.2.2.4 Visit 5 (Day 21 ± 3 days)

Study site personnel will contact the subject/legally authorized representative via telephone to assess for the occurrence of AEs, use of concomitant medications, compliance with study drug administration, and completion of subject diary or PK subject diary. A Phone Contact Form for the telephone contacts to obtain safety and compliance information will be provided to all sites (see Section 16.1). If any safety concern arises, subjects may return to the study site for an Unscheduled Visit.

Subjects consenting to optional PK assessments will be reminded to withhold taking the morning dose of study drug on the day of Visit 6; subjects not consenting to optional PK assessments may take their study drug on the day of Visit 6 as instructed.¹²⁸

9.2.2.5 Visit 6 (Day 30 ± 3 days)

- Assessment of Chagas' disease signs and symptoms (to be performed during physical examinations); see Section 9.4.4
- Concentration test for *T. cruzi* (subjects < 8 months of age), conventional and nonconventional serologic testing for Chagas' disease and qPCR

¹²⁴ Text modified as per Amendment 4

 $^{125\ {\}rm Text}\ added/deleted/modified\ for\ clarity\ and\ to\ reflect\ changes\ made\ per\ Amendment\ 1$

¹²⁶ Text modified as per amendment 4

¹²⁷ Text modified for clarity and per Modifications 6 and 8 (Amendment 1)

¹²⁸ Text modified for clarity and per Modifications 6 and 8 (Amendment 1)

03 NOV 2020

Page: 55 of 259

- Assessment of AEs
- Concomitant medications
- Brief physical examination, including assessments of heart, lungs, and abdomen, the skin for the presence of severe dermatitis, and clinical assessments for the presence of peripheral neuropathy. Abnormal findings will be documented as AEs (see Section 9.6.1.1).
- Neurological examination (see Section 9.6.3.3). Abnormal findings will be documented as AEs (see Section 9.6.1.1).
- Vital signs (blood pressure is optional in subjects < 5 years of age at the discretion of the investigator)
- 12-lead ECG (optional in subjects < 5 years of age at the discretion of the investigator).
- Serum hematology and chemistry, coagulation, and urinalysis (if urine specimen can be obtained). Fasting is dependent on the age of the subject at the discretion of the investigator.
- Urine pregnancy test on all females of childbearing potential (i.e., those who have experienced menarche). Any subject with a positive urine pregnancy test will have a serum pregnancy test to confirm results; if pregnancy is confirmed, the subject is to be discontinued from the study and undergo all study assessments as described in the EOT Visit.
- For subjects consenting to PK assessments, a pre-dose PK blood sample will be obtained (see Table 9–1).
- Administer study drug with food to subjects consenting to PK assessments (who withheld their morning dose of study drug) and instruct subject on completion of PK diary, according to the instructions provided on the PK subject diary.¹²⁹
- For subjects consenting to PK assessments, post-dose PK blood samples will be obtained (see Table 9–1). At the 2 4 hour time point (i.e., at the time of C_{max}), an ECG will be obtained.
- Collect and dispense study drug and diary. At this visit, subjects will return all remaining study drug and empty packaging, and study drug for the remaining 30 days of treatment will be dispensed.
- Drug accountability and review of diaries for study drug compliance
- Collect and dispense pre-paid phone card to facilitate contact between study site personnel and the subjects/subjects' authorized representatives at Visit 7.¹³⁰

¹²⁹ Text modified as per amendment 4

¹³⁰ Visit 6 assessments added per changes made per Amendment 1

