6.3.1 Withdrawal

Withdrawal criteria

Subjects *must* be withdrawn from the study if any of the following occurs:

• At their own request or at the request of their parents' or legally acceptable representative. At any time during the study and without giving reasons, a subject may

	Integrated Clinical Study Protocol	
	BAY A2502 / 16027	
03 NOV 2020	Version 11.0	Page: 40 of 259

decline to participate further. The subject will not suffer any disadvantage as a result of this decision.

- Pregnancy. If any urine pregnancy test is positive, a serum pregnancy test must be performed to confirm the result. See Section 9.6.2.⁹⁴ (not applicable to part 2)
- Subjects, with positive parasitology test at the 30-day visit for whom (1) it has been determined that the drug was administered correctly and (2) the daily dosage given was correct, must be discontinued from the study and treated with an alternative trypanocidal medication, selected by the investigator.⁹⁵ (not applicable to part 2)

Subjects *may* be withdrawn from the study if any of the following occurs:

- If, in the investigator's opinion, continuation of the study would be harmful to the subject's well-being
- At the specific request of the sponsor and in liaison with the investigator (e.g., obvious non-compliance, safety concerns)
- For the following situations that are regarded by the investigator to be related to the use of study drug (nifurtimox) (not applicable to part 2):
 - Severe nervous system disorders such as seizure, vertigo/dizziness, polyneuropathy, or peripheral neuropathy
 - Severe gastrointestinal disorders, severe decreased appetite
 - Significant loss of body weight in the judgment of the investigator
 - Severe hepatic impairment
 - Severe renal impairment
 - Psychic disorders such as disorientation, psychotic behavior
 - Development of malignant disease
 - Hematological abnormalities such as severe leukopenia

Depending on the time point of withdrawal, a withdrawn subject is referred to as either "screening failure" or "dropout" as specified below:

Screening failure

A subject who, for any reason (e.g., failure to satisfy the selection criteria), terminates the study before the time point used for the definition of "dropout" (see below) is regarded as a "screening failure."

Re-starting the defined set of screening procedures to enable the "screening failure" subject's participation at a later time point is allowed only in the following situations (not applicable to part 2):

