03 NOV 2020

Version 11.0

Page: 47 of 259

Table 9–1: Schedule of procedures and assessments in part 1 – Study 16027

Phase	Screening			т	reatment	Phase			Follow-up Phase		
Visit	1	2	3	4 ^a	5 ^a	6	7 a	8 (EOT) ^b	9	10	11
Day	-14 to -1	1 ^c	7 ± 1	14 ± 1	21 ± 3	30 ± 3	42 ± 3	60 ± 3	90 ± 7	240 ± 7	420 ± 7
Initiation procedures							11				
Informed consent/assent	•										
Demographics (sex, age)	•										
Medical/surgical history	•										
Inclusion/exclusion criteria	•	•									
Efficacy											
Assessment of Chagas' disease signs and symptoms ^d	•		•			•		•	•	•	•
Concentration test for T. cruzi (subjects < 8 months of age)	•		•			•		•	٠		
Conventional and non-conventional serologic testing for	•		•			•		•		•	
Chagas' disease ^e	•		•			•		•		•	•
qPCR ^e	•		•			•		•		•	•
Indirect hemagglutination assay (IHA) *	•										•
Safety											
Adverse events	•	•	•	•	•	•	•	•	•	•	•
Concomitant medication	•	•	•	٠	•	•	•	•	•	•	•
Physical examination ^f	•		•			•		•	•	•	•
Neurological examination ^g	•		•			•		•			
Vital signs (heart rate, RR, BP, temperature), height/length,	•	•	•			•		•	•	•	
and weight h	•	•	•					•	•	•	•
12-lead ECG ⁱ	•	•	•			•		•	•	•	•
Serum hematology, chemistry, and coagulation ^j	● ^k		•			•		•	•		
Urinalysis (if specimen can be obtained)	●k		•			•		•	•		
Urine pregnancy test ¹	•	•	•			•		•	•		
Pharmacokinetics											
PK blood sampling (optional) ^m		•	•			•		•			
Study Treatment											
Study drug administration ⁿ		•				•					
Study drug and diary dispensed °		•				• p					
Study drug and diary collected			•			• p		•			
Study drug accountability/review compliance			•	•	•	•	•	•			
Dispense pre-paid phone card ^q			•			•					
Collect pre-paid phone card						•		•			

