9.6.1.6 Adverse events of special safety interest

In this study, all AEs of weight loss of > 20%, severe rash, and severe polyneuropathy will be considered AEs of special safety interest.¹⁶⁸ Adverse events of special safety interest will be assessed, monitored, and reported as described in Section 9.6.1.4.

¹⁶⁷ Revised since Investigators' Brochure became available to serve as the reference document for nifurtimox (Amendment 1)

03 NOV 2020 Version 11.0

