10.3 Variables and planned statistical analyses

10.3.1 Variables

10.3.1.1 Part 1 (CHICO)

The primary efficacy variable will be sero-reduction or sero-conversion at 12 months post-treatment using two conventional ELISA serology tests as the measure of efficacy. This sero-reduction or sero-conversion is considered cure, and the primary variable is binary (cure, no cure).

In the event of discordancy between the two conventional ELISA test results, the following will be considered:

- For sero-reduction, the average percentage of OD reductions will be used (e.g., Test #1 = 15% and Test #2 = 25%; average = 20% and, hence, cure).
- For sero-conversion, only when both test results are negative the subject is considered as negative (cure).¹⁸¹

Secondary efficacy variables include clinical signs/symptoms of Chagas' disease, concentration test for *T. cruzi* (subjects < 8 months of age at randomization), conventional and non-conventional serologic testing, and disease state determined by qPCR.

Background variables include demographics (sex, age), height/length, weight, medical/surgical history, and medication history.

Safety variables include AEs, physical examination abnormalities, vital signs, ECG abnormalities, hematology and blood chemistry, coagulation, and urinalysis.¹⁸²

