03 NOV 2020

Version No. 11.0

Page: 182 of 259

New table:

Table 9-1: Schedule of procedures and assessments – Study 16027

Phase	Screening			т	reatment	Phase			Fo	llow-up Ph	ase
Visit	1	2	3	4 ^a	5 a	6	7 ^a	8 (EOT) ^b	9	10	11
Day	-14 to -1	1 ^c	7 ± 1	14 ± 1	21 ± 3	30 ± 3	42 ± 3	60 ± 3	90 ± 7	240 ± 7	420 ± 7
Initiation procedures			1								
Informed consent/assent	•										
Demographics (sex, age)	•										
Medical/surgical history	•										
Inclusion/exclusion criteria	•	٠									
Efficacy											
Assessment of Chagas' disease signs and symptoms ^d	•		•			٠		٠	•	•	•
Concentration test for T. cruzi (subjects < 8 months of age)	•		•			٠		•	•		
Conventional and non-conventional serologic testing for	•					•		•			
Chagas' disease ^e	•		•			-		•		•	•
qPCR	•		•			•		•		•	•
Safety											
Adverse events	•	•	•	•	•	•	•	•	•	•	•
Concomitant medication	•	•	•	•	•	•	•	•	•	•	•
Physical examination ^f	•		•			•		•	•	•	•
Neurological examination ^g	•		•			•		•			
Vital signs (heart rate, RR, BP, temperature), height/length, and weight $^{\rm h}$	•	•	•			•		•	•	•	•
12-lead ECG ⁱ	•	•	•			٠		•	•	•	•
Serum hematology, chemistry, and coagulation ^j	●k		•			۲		•	•		_
Urinalysis (if specimen can be obtained)	●k		•			٠		•	•		
Urine pregnancy test	•	٠	•			٠		•	•		
Pharmacokinetics											
PK blood sampling (optional) ^m		٠	•			٠		•			
Study Treatment											
Study drug administration ⁿ		٠				٠					
Study drug and diary dispensed °		•				● p					
Study drug and diary collected			•			● p		٠			
Study drug accountability/review compliance			•	•	•	•	•	•			

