## **Adverse Events**

All adverse events occurring during the study (i.e., from signing of informed consent until last visit) will be reported. The MedDRA coding system will be used to code the adverse events.

An overview of frequencies of subjects who died, experienced any adverse event, experienced any drug-related adverse event, experienced a serious adverse event (SAE), experienced a drug-related serious adverse event, or discontinued due to an adverse event will be summarized by treatment regimen.

Adverse events will be considered treatment emergent, if they first occurred or worsened at or after first application of study medication during the course of the study up to and including 7 days after last application of study medication.

Incidence of treatment emergent AEs (TEAEs), drug-related TEAEs, serious TEAEs, drugrelated serious TEAEs, as well as TEAEs leading to discontinuation will be summarized by primary system organ class and high level term by treatment regimen.

The definitions of incidence are as follows:

- Incidence of all events: # of subjects reporting the event with a start date during or after treatment/# of subjects valid for safety.
- Incidence of drug-related events: # of subjects reporting a drug-related event with a start date during or after treatment/# of subjects valid for safety.
- Incidence of events by maximum intensity: # of subjects reporting the event at the indicated intensity with a start date during or after treatment/# of subjects valid for safety.

Adverse events leading to death, premature discontinuation and serious adverse events will be listed. In this study, all AEs of urticarial, weight loss of > 20%, severe rash, and severe polyneuropathy will be considered AEs of special safety interest. Adverse events of special safety interest will be summarized by treatment regimen.

AEs occurring between the time of consent and the first dose of study drug will be summarized separately.

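### The Visit 6 (Day 30) list and Table 9-1 disagree on whether weight is taken, and the SAP counts weight loss above 20% only from adverse event reports, never from measured weights

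*Protocol*

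**What the plan says.** **Visit 6 text.** In Protocol 9.2.2.5 the item reads "Vital signs (blood pressure is optional in subjects < 5 years of age at the discretion of the investigator", the bracket closes, and the line ends. The lists for Visits 1, 2, 3, 8, 9, 10 and 11 open with the same words but continue. Visit 3, for example, has "Vital signs (blood pressure is optional in subjects < 5 years of age at the discretion of the investigator), height/length, and weight".

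**Schedule table.** Table 9-1 has one combined row, "Vital signs (heart rate, RR, BP, temperature), height/length" and weight, with a mark at Visit 6. Section 9.6.3.4 names the visits for vital signs, Visit 6 among them. For height and weight it says how they are taken but not when.

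**Safety role of weight.** Protocol 9.6.1.6 states that "all AEs of weight loss of > 20%, severe rash, and severe polyneuropathy will be considered AEs of special safety interest". Section 6.3.1 lists, among the reasons for which a subject may be withdrawn, "Significant loss of body weight in the judgment of the investigator".

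**Analysis.** Protocol 10.3.1.1 puts weight with the background data: "Background variables include demographics (sex, age), height/length, weight, medical/surgical history, and medication history". SAP 4.3 does the same, and the list of Part 1 safety variables in SAP 6.3 does not name weight. For the weight-loss event the SAP says only that "Adverse events of special safety interest will be summarized by treatment regimen". SAP 4.1 adds a general rule that all collected variables are summarized descriptively at each assessment time, by age stratum and regimen.

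**The concern.** Visit 6 is the only on-site visit between Day 7 and Day 60. It is also the day on which the 30-day arm changes from active drug to placebo. In that arm the Day 60 weight comes after about 30 days without active drug, so a loss reached by Day 30 may have recovered by then. Where there is no Day 30 weight, the two regimens are compared on weights taken at different times since the last active dose.

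The SAP gap is a separate matter. The event of interest is a percentage change in a quantity that the trial measures. If it is counted only from filed reports, its incidence depends on whether an investigator compared two weights and recorded an event. A coded event term also carries no percentage, so the SAP does not show how reports above 20% would be separated from other weight-loss reports. At stake is the completeness of one named safety event. The primary efficacy result is not touched.

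**Working it through.** The plan gives no figure of its own here, so the check compares passages and counts days.

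**Step 1: does Table 9-1 schedule weight at Visit 6?** The combined row runs over two lines in the text, and the second line, which ends with weight, shows no Visit 6 mark of its own. The same row is printed unbroken in the Amendment 2 text (Section 15.2.2) as "Vital signs (heart rate, RR, BP, temperature), height/length, and weight", marked at Visits 1, 2, 3, 6, 8, 9, 10 and 11. That print is used only to read the broken row, not as evidence of a contradiction. The current table therefore schedules weight at Visit 6, and the current Section 9.2.2.5 does not list it.

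**Step 2: gaps between scheduled site weights.** Inputs from the visit headings: Visit 3 on Day 7 ± 1, Visit 6 on Day 30 ± 3, Visit 8 on Day 60 ± 3. The nominal gap is the later day minus the earlier day. The shortest gap is the earliest later day minus the latest earlier day, and the longest is the reverse.

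| Reading | Interval | Nominal | Shortest | Longest |
|---|---|---|---|---|
| Visit text | Visit 3 to 8 | 60 − 7 = 53 | 57 − 8 = 49 | 63 − 6 = 57 |
| Table 9-1 | Visit 3 to 6 | 30 − 7 = 23 | 27 − 8 = 19 | 33 − 6 = 27 |
| Table 9-1 | Visit 6 to 8 | 60 − 30 = 30 | 57 − 33 = 24 | 63 − 27 = 36 |

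The conflict concerns one scheduled weight. Without it, the longest nominal gap on treatment is 53 days instead of 30.

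**Step 3: what falls inside the gap.** Calls take place on Days 14, 21 and 42. The Part 1 Phone Contact Form (Section 16.1.1) asks whether the child has lost weight since the last visit and, if so, the current weight. This is a caregiver's report, and a figure is requested only after a yes. A safety concern may lead to an unscheduled visit. Under SAP 4.5, however, unscheduled post-baseline values are not used even where the scheduled value is missing, so a weight taken then would not enter the by-visit summaries.

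**Step 4: can the planned summaries show the event?** The SAP 4.1 rule yields means, medians, minimums and maximums by visit. In a stratum that spans 2 years to under 18 years, these do not show whether any one child lost more than 20% of baseline weight. That needs each child's own change, 100 × (weight at visit − baseline weight) / baseline weight, and a count of values below −20. The SAP specifies neither.

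**The case against.** **The schedule governs.** Section 9.1 presents Table 9-1 as the schedule of procedures, and a site that follows it weighs the child at Day 30. This stands: the 53-day gap is conditional. Section 7.4, which keeps the Visit 6 dosage unchanged even if weight has changed, is consistent with a weight being known then but does not require one. A site that works from 9.2.2.5 is still following a current protocol section.

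**Other safeguards exist.** The phone form asks about weight loss three times within the gap. Visit 6 keeps its adverse event assessment and physical examination. A loss that persists would show at Visit 8 or Visit 9. This also stands, and limits the exposure to transient loss and late detection.

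**The event is defined as an adverse event.** Protocol 9.6.1.6 describes a class of adverse events, so counting reports follows that definition. This is correct: the SAP does not contradict the Protocol. The point is that a count from measured weights would check the reported one, and the plan has no such check.

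**Stronger readings that do not hold.** A reader might infer that weight loss goes unmeasured from Day 7 to Day 60 throughout the trial. Table 9-1 does not support that, and the calls mean that weight loss is not left unasked. A reader might also infer that 53 of the 60 treatment days lose their measurement. Weights are taken only on visit days under either reading, so 53 is the length of an interval, not a number of lost measurements. Nor is a measured withdrawal threshold left without data: that item is a matter of investigator judgement, is permissive, and carries no percentage.

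**Conclusion.** The concern holds in two limited parts. First, Protocol 9.2.2.5 and Table 9-1 conflict on height/length and weight at Visit 6. Where the visit text is followed, the longest gap between scheduled site weights on treatment is 53 days (49 to 57) instead of 30 (24 to 36), with only caregiver reports in between. Second, the SAP has no count of losses above 20% from measured weights and relies on filed reports.

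The first part assumes that some sites follow the visit text; the documents do not say how many. It also rests on reading the two-line table row as one row. The second part needs neither assumption. How many children would be affected cannot be worked out from the documents. The matter is worth correcting because it concerns a named event of special safety interest, the data are already scheduled under Table 9-1, and the correction is small.

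**What to change.** Reconcile Protocol 9.2.2.5 with Table 9-1 on height/length and weight at Visit 6. Which passage prevails is for the sponsor to decide.

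In SAP 6.3, derive each child's percentage change from baseline weight at each scheduled visit, with baseline as defined in SAP 4.5. Tabulate by regimen and age stratum the number with a measured loss above the documents' own 20% threshold, next to the number with that event reported as an adverse event. Give the number weighed at each visit as the denominator.

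The cost is one line of protocol text and one descriptive table, with no new procedure beyond those in Table 9-1. If Part 1 visits are already complete, the text change recovers no weights, but the table can still be made from the data collected, and the number weighed at Visit 6 would show how complete they are.
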